4.4.3. Missing continuous data

If there is a missing value in the tabulation of continuous data, it will be excluded from the tabulation. If continuous data are available at multiple time points, only the missing time points will be excluded. If continuous data are classified into categories, follow "4.4.4 Categorical Data."

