4.4.5. Date Variables

Imputation of date variables will be handled as follows.

< End date of administration of this drug >

- ✧ If the number of doses of this drug is once, imputation will use the start date of this drug administration.

< Adverse events >

- ✧ If the date of onset and date of outcome are missing, they will not be imputed and will be handled as unknown.

< Prior treatment drugs/Prior treatment (other than drugs)/Concomitant drugs >

- ✧ Only systemic steroids for SLE have a date but if the last record is ' Dosing Continued ', then it will be imputed with the last date from this drug Administration Status.

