4.10. Responders

A responder is defined as a case where this drug treatment start date and post-treatment assessments are present and the following conditions are met:

Efficacy assessments	Responder definition
SELENA SLEDAI (Used for calculation of efficacy percentage)	≥ 4 decrease in score from baseline
PGA score	≥ 0.3 (10 mm) decrease from baseline
LLDAS (Lupus Low Disease Activity State)	1. SELENA-SLEDAI ≤ 4 and no major active organ involvement (renal, central nervous system, cardiopulmonary, vasculitis, pyrexia) on SELENA-SLEDAI, without hemolytic anemia or active gastrointestinal lesions reported as adverse events.
	2. No new signs or symptoms as compared to the last SELENA-SLEDAI assessment.
	3. PGA score ≤ 1 (33 mm)

Efficacy assessments	Responder definition
	4. Corticosteroid dose ≤ 7.5 mg/day at time of assessment
	5. Use of the same immunosuppressant as compared with prior medication. No unapproved drugs of rituximab, anifrolumab, ustekinumab, or baricitinib are used as concomitant medications. The use of anifrolumab with this drug initiated on 2021/9/27 or later is allowed.
LLDAS Adverse Events	Haemolytic anaemia: 10018916 (PT code) Active gastrointestinal lesions: to be defined in a separate document
Corticosteroid Reduction at Week 40~52	Average daily dose Proportion of patients who were able to reduce their average daily steroid dose by $\geq 25\%$ and ≤ 7.5 mg/day from baseline at Week 40~52 (in patients with baseline average daily steroid dose > 7.5 mg/day). Subjects who discontinued or completed administration of this drug before Week 52 will be classified as non-responders.

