4.12. Average daily steroid dose

The average daily steroid dose will be prednisolone-equivalent (prednisolone conversion table: to be defined in a separate document) and the average daily steroid dose during the 7 days prior to and including the day of evaluation will be used. The mean value during the 7 days before treatment including the dose on the first day of treatment will be used as the baseline. If there is no information on steroid administration during the observation period, it will be handled as "0 mg." Data obtained after the end date of administration of this drug will not be used for tabulation.

The prednisolone conversion table will be updated when new drugs are added and fixed with the data at the time of DBF.

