6.4.11. Cumulative steroid dose (Table 3.14)

Analyzed: Efficacy analysis population

Analysis details: For cumulative steroid dose, summary statistics will be calculated.

6.4.12. Time-course plots for the proportion of responders in SELENA SLEDAI score, PGA score, and LLDAS (Figure 3.0x)

Analyzed:	Efficacy analysis population
Analysis details:	For each efficacy endpoint (SELENA SLEDAI score, PGA score, LLDAS), responder rates will be calculated over time and bar charts will be prepared. The denominator for the responder rate is the number of patients. Additionally, for the Lupus Impact Tracker, a bar chart of mean + standard deviation will be produced over time.
Chronological order:	Week 24, Week 52, and at discontinuation/completion (LOCF) (SELENA SLEDAI score, PGA score, LLDAS)

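### SAP 4.12 reads absent steroid information as 0 mg and SAP 4.4.5 closes ongoing steroid records at the last Benlysta date, leaving Week-52 steroid results either falsely low or unevaluable for some continuing patients

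*SAP*

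**What the plan says.** - **Dose definition (SAP 4.12).** The dose is expressed as prednisolone equivalent, and "the average daily steroid dose during the 7 days prior to and including the day of evaluation will be used".
- **Absent information (SAP 4.12).** "If there is no information on steroid administration during the observation period, it will be handled as" 0 mg.
- **Cut-off (SAP 4.12).** "Data obtained after the end date of administration of this drug will not be used for tabulation".
- **Ongoing steroid records (SAP 4.4.5).** If the last systemic steroid record is marked 'Dosing Continued', "then it will be imputed with the last date from this drug Administration Status".
- **General rule (SAP 4.4.3).** "If there is a missing value in the tabulation of continuous data, it will be excluded from the tabulation". SAP 4.4.1 allows no imputation beyond the SELENA SLEDAI and PGA rule in 4.4.2.
- **Uses of the dose (SAP 4.10).** LLDAS criterion 4 is "Corticosteroid dose ≤ 7.5 mg/day at time of assessment". The Week 40-52 steroid endpoint needs an average daily dose at least 25% below baseline and no higher than 7.5 mg/day, in patients who start above 7.5. For that endpoint, "Subjects who discontinued or completed administration of this drug before Week 52 will be classified as non-responders".
- **What the CRF holds (Protocol section 8, item 7).** Presence or absence of systemic steroid use is collected, with dose and duration.

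**The concern.** Two things are mixed. A patient recorded as not taking steroids has a dose of 0 mg. A patient whose steroid record is blank has an unknown dose. The CRF can tell them apart, but SAP 4.12 does not. SAP 6.2.1 has an unknown class beside 0 for the dose at the start of treatment, so the plan recognises the difference at baseline but not afterwards.

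The closing rule adds a second gap. A record marked as continuing says that the patient was still on steroids, yet it ends at a Benlysta date. For patients still on Benlysta, that date can fall before the Week-52 steroid window or the Week-52 visit. The SAP does not say whether the days in between are 0 mg or missing.

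Steroid dose and LLDAS are named effectiveness outcomes in Protocol section 9. Two programmers could follow this SAP faithfully and report different rates.

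**Working it through.** The plan states no figure to reproduce for this point except its visit window, which checks: Day 365 ± 28 gives Days 337 to 393, or 57 days (SAP 4.13.1).

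**Step 1. The 0 mg rule alone.** SAP 4.6 judges items other than adverse events by whether detail is present. Its closing line on drug checkboxes refers back to what precedes it, and could mean either that rule or the table above it, in which a yes without detail becomes unknown. On the first reading, a steroid user with no detail record has no steroid information, receives 0 mg and passes criterion 4. No closing-date argument is needed.

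**Step 2. Who can have an uncovered Week-52 window.** SAP 4.18 keeps a patient recorded as continuing in that class if the end date is no earlier than 52 weeks minus 28 days. With 52 weeks = Day 364 (SAP 4.5), this is 364 − 28 = Day 336. The Week-52 steroid window is Days 358-364 (SAP 4.13.2). A record closed on any of Days 336-357 leaves all seven days uncovered.

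**Step 3. LLDAS criterion 4 at the Week-52 visit.** For a visit on Day v, the averaging window is Days v − 6 to v. With closure on Day E, covered days = E − (v − 6) + 1, limited to 0-7.

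| Record closed on | Visit days with no covered day | Share of the 57-day window |
|---|---|---|
| Day 336 | 343-393 | 51 of 57 |
| Day 357 | 364-393 | 30 of 57 |
| Day 364 | 371-393 | 23 of 57 |

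These are shares of calendar days, not of patients. If uncovered days count as 0 mg, any true dose passes criterion 4 at those visits. With closure on Day 364 and a visit on Day 365, six of seven days are covered, so an unchanged dose up to 7.5 × 7/6 = 8.75 mg/day passes. If uncovered days are excluded, a visit with no covered day has no dose.

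**Step 4. Week 40-52 endpoint.** The SAP does not say how this average is formed. Assume the mean of the four 7-day windows in SAP 4.13.2: Weeks 40 (Days 274-280), 44 (302-308), 48 (330-336) and 52 (358-364). With closure on Days 336-357, the first three are fully covered and the fourth is empty.

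- Uncovered days as 0 mg: (1 + 1 + 1 + 0)/4 = 0.75 of the true dose, an apparent reduction of exactly 25%. The upper limit is met when 0.75 × dose ≤ 7.5, so dose ≤ 10 mg/day. An unchanged dose above 7.5 and up to 10 mg/day is a responder.
- Uncovered days excluded: (1 + 1 + 1)/3 = 1, an apparent reduction of 0%.
- Partial coverage, closure on Day 360, uncovered days as 0 mg: (3 + 3/7)/4 = 0.857, a reduction of 14.3%, below the 25% limit.

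**Step 5. Cumulative dose.** SAP 6.4.11 says only: "For cumulative steroid dose, summary statistics will be calculated". With data cut at the Benlysta end date and no time denominator, an illustrative constant 10 mg/day totals 10 × 100 = 1,000 mg for a patient who stops at Day 100 and 10 × 364 = 3,640 mg at Day 364.

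**The case against.** The strongest reply is that exclusion is the better reading. The 0 mg rule is limited to the observation period, which Protocol section 6 ends at 52 weeks or at withdrawal. The cut-off sentence drops data after the Benlysta end date, SAP 4.4.3 excludes missing time points, and SAP 6.4.9 labels its dose table as observed. The 0 mg rule may also mean only patients with no steroid record at all. On this reading no false 0 mg arises from closing a record.

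Much of this stands, but it does not settle the matter. For a patient still on Benlysta, Days 358-364 lie inside the 52-week observation period. Exclusion also has a cost: patients whose CRF says steroids continued have no Week-52 dose, and the SAP does not say how LLDAS is then scored.

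Stronger readings are tempting and are not supported:

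- *Early stoppers are counted as steroid-sparing responders.* SAP 4.10 already makes them non-responders at Week 40-52.
- *Discontinuation visits read as 0 mg.* SAP 4.13.1 appears to date that assessment at the discontinuation or completion date, so an ongoing record would cover it.
- *Patients still on steroids are counted as reaching LLDAS.* A 0 mg value meets one criterion; the other four still apply.
- *The false reduction is about 30% and reaches doses near 11 mg/day.* This needs an average over every day, which the SAP does not define. Over Days 274-364 with closure at Day 336, it would be 1 − 63/91 = 30.8%; with closure at Day 350, only 1 − 77/91 = 15.4%.
- *All steroid results are biased toward benefit.* For the closing rule, that follows only if uncovered days count as 0 mg.

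**Conclusion.** The point holds in limited form. SAP 4.12 does not separate recorded non-use from a missing record and is not reconciled with 4.4.1 and 4.4.3. The closing rule in 4.4.5 leaves some continuing patients without Week-52 steroid data, and either way of treating the gap is unsatisfactory: a false low dose, or loss of patients known to be on steroids.

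The size is conditional. The 25% apparent reduction and the 10 mg/day ceiling require uncovered days to count as 0 mg, the Week 40-52 value to be the mean of four windows, and an end date on Days 336-357 in a patient handled as continuing. The last date in the administration status may be the end of a recorded period rather than the last dose, in which case fewer records close early. The number of patients affected cannot be computed from the documents.

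Severity is moderate. There is no comparator, the steroid and LLDAS results are descriptive, and the response rate by patient characteristic uses SELENA SLEDAI (SAP 6.4.1).

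**What to change.** - **SAP 4.12:** use 0 mg only where the CRF records no steroid use or a steroid stop date. Otherwise treat the value as missing. State how the 7-day mean is formed when part of the window is uncovered, and how LLDAS is scored when criterion 4 cannot be evaluated.
- **SAP 4.4.5:** for patients continuing Benlysta, carry a 'Dosing Continued' steroid record to the end of that CRF's observation period (Day 168 or 364, following SAP 4.5) or to the assessment date. Align the cut-off sentence in 4.12; otherwise it would remove the carried days again.
- **SAP 4.10:** define the Week 40-52 average, and say whether patients handled as continuing with an end date before Day 364 fall under the non-responder rule.
- **Consistency:** reconcile 4.4.1, 4.4.3, 4.4.5 and 4.12, and clarify the checkbox line in 4.6.
- **Optional:** show cumulative dose (6.4.11) per day observed, because totals cut at the Benlysta end date are not comparable between early stoppers and completers. Tabulate LLDAS and steroid dose with the affected patients excluded, to show the size of the effect.

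The cost is SAP wording and a change to the derivation, with no new data. The downside is somewhat less favourable figures and some missing values.

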4.13. Assessment window

4.13.1. Efficacy assessments and laboratory data

Visit * information, as defined below, will be used in the analysis. If a visit with an evaluation date (including unscheduled visit) closer to the specified date is adopted and the period from the specified date is the same, the latest visit will be adopted. If there are multiple visits to be adopted, the visit to be adopted shall be defined after discussion at the case review meeting.

The evaluation date (calculation) is calculated as follows.

Date of evaluation (calculation) = Target date (or date of discontinuation/completion of this drug treatment)
- start date of this drug treatment +1

Evaluation time point	Scheduled date	Acceptable range (+/- days)	Duration (days)	
			to	Until
24 weeks after start of administration of this drug	169	28	141	197

Planned analysis: 207735

Version.13.0

date 2024/09/30

52 weeks after start of administration of this drug	365	28	337	393
--	-----	----	-----	-----

*Visit indicates the time of assessment

4.13.2. Systemic corticosteroids for SLE

Visit information, defined below, will be used in the analysis.

The evaluation date (calculation) is calculated as follows.

Date of evaluation (calculation) = Target date - Start date of this drug treatment +1

Evaluation time point	Date of Assessment (day)	Duration (days)	
		to	Until
Week 2	14	8	14
Week 4	28	22	28
Week 8	56	50	56
12 Week	84	78	84
Week 16	112	106	112
Week 20	140	134	140
Week 24	168	162	168
Week 28	196	190	196
Week 32	224	218	224
Week 36	252	246	252
Week 40	280	274	280
Week 44	308	302	308
Week 48	336	330	336
Week 52	364	358	364

4.14. Definition of Same Case

Identical cases are defined as follows. The details will be examined when they become known.

Hospital transfer: When a patient is transferred to another hospital and visits more than one medical institution and is found to be the same patient.

Co-examination: When the same or multiple physicians examined the same patient at multiple medical institutions in collaboration.

Duplicate case: Duplicate entries of the same information are found in the same patient.

4.16. Safety specification

Safety specifications will be made in accordance with the investigation plan.

4.17. Handling of fixed cases by volume

Data of fixed cases and each volume will be used as CRF data. (If Volume 1 is locked, the patient will be classified as a "locked patient," but data from CRFs from which subsequent volumes are not locked will not be used in analyses.)

For tabulation of "subjects who completed the observation period," refer to the definition of "subjects who completed the observation period (interim analysis)" in analysis sets/sites in 4.2.

4.18. Handling of treatment continuation/discontinuation/completion

Regardless of the description in the survey form, "patients who completed the observation period" will be handled as follows and tabulated.

Treatment Disposition for this drug	Administration end date	Handling
Treatment continued	< Week 52	Treated as patients who

	-28 (days)	discontinued/completed treatment Reason for discontinuation/completion should be "Unknown "
	≥ 52 weeks -28 (days)	Treatment continued (No change)
Discontinuation/completion of treatment	< Week 52	Discontinuation/Completion of Treatment (No Change)
	≥ 52 weeks	They will be handled as patients continuing treatment, and the described reasons for discontinuation/completion of treatment will not be used.

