4.2. Analysis sets/sites

Item	Definition
Registered sites	Sites for all registered patients (patients eligible for registration). Sites with patients registered before the data lock date (excluding duplicate site codes).
Enrolled patients	Patients enrolled within the enrollment period specified in the protocol (from December 13, 2017 to the date of lifting of approval conditions) (registration-eligible patients). Subjects with an enrollment date before the data lock date.
Patients with locked CRF	All registered patients whose CRFs were collected and locked. Cases that have a recall date and a processing completion date and the processing completion date is before the data lock date.
Safety analysis population	Patients with locked CRFs who do not correspond to patients excluded from the safety analysis set (see 4.3.1)
Efficacy analysis population	Patients in the safety analysis set who are not excluded from the efficacy analysis set (see 4.3.2)
CRF collection target patients (Approval condition lifting)	Reports on registered patients whose CRFs were collected and patients eligible for CRF collection were identified (administration of this drug was started by October 31, 2018). The start date of administration of this drug (registration form) shall be the date of registration form.
Sites that can publish	PMW sites that are “11 _ Publication allowed (already concluded) ” or “ 13_ Publication allowed (no change required) ” and sites that are confirmed as “21 _ Being confirmed ” to be “ Publication allowed ”

Item	Definition
Subjects who completed the observation period (Interim analysis)	
< Subjects falling under Population A >
 
Disclosure-ready patients meeting any of the following conditions among patients treated with this drug before October 31, 2018 at study sites
 
 • Completed up to Week 52: Separate Volume 1 (official approval) and Separate Volume 2 (official approval) • Completed as discontinued: Volume 1 (official approval) in which the reason for discontinuation is described is official approval (excluding official approval of Volume 2 only) • Completed as discontinued (logic assessment): Separate volume 1 (official approval) and Separate volume 2 is “Unnecessary ” or“ Unable to collect ” 
< Subjects falling under Population B >
 
This falls under “patients with depression-related events ” among patients whose CRFs were additionally collected and are specified in a separate document.

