4.5. Treatment Disposition Date for Continued Treatment

The end date of administration in the case of continued administration will be imputed with the last date of administration in this drug administration status. However, if the administration status of this drug is blank, it will be handled as follows.

Date of completion of treatment = date of initiation of treatment + < number of days considered to be converted > -1

Deemed equivalent number of days

24 weeks → 168 days (when only CRF 1 is collected)

52 weeks → 364 days

*If the end date of administration calculated above is after the end date of the contract period, it will be

complemented with the end date of the contract.

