Analysis details:	According to "4.18 Handling of treatment continuation/discontinuation/completion," the data will be output by the number of patients with treatment discontinuation/completion, the reason for treatment discontinuation/completion, and the duration (weeks) of treatment with this drug until discontinuation/completion for the patients who discontinued/completed the treatment with this drug. Reasons for discontinuation/completion will be regarded as overlapping. A Kaplan-Meier plot (discontinuation rate) of time to discontinuation of this drug will be generated. In addition, a Kaplan-Meier plot of the extension period of this drug (continuation rate) will be provided.
Duration (weeks) of administration of this drug until discontinuation/completion of administration:	
 • <2, 2 ≤ to <4, 4 ≤ to <8, 8 ≤ to <12, 12 ≤ to <16, 16 ≤ to <20, 20 ≤ to <24, 24 ≤ to <28, 28 ≤ to <36, 36 ≤ to <44, 44 ≤ to <52, 52 ≤, unknown

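### SAP 4.18 recodes some patients last recorded as on treatment as discontinued; this raises the Kaplan-Meier discontinuation curve above the censored estimate, and no count or sensitivity curve is planned

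*SAP*

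**What the plan says.** SAP 4.18 applies to patients who completed the observation period and takes effect "Regardless of the description in the survey form". It has two rules that change status:

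- A patient recorded as continuing, with an end date earlier than Week 52 minus 28 days, is handled as "discontinued/completed treatment Reason for discontinuation/completion should be" Unknown. Continuing patients at "≥ 52 weeks -28 (days") are left as they are.
- A patient recorded as stopping at or after 52 weeks goes the other way: "They will be handled as patients continuing treatment, and the described reasons for discontinuation/completion of treatment will not be used".

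SAP 4.17 refers to SAP 4.2 for who completed the observation period. One route in is "Completed as discontinued (logic assessment): Separate volume 1 (official approval) and Separate volume 2 is" either unnecessary or unable to be collected. SAP 4.5 sets a continuing patient's end date to the last date in the administration status. Only if that is blank does it use a deemed duration: "24 weeks → 168 days (when only CRF 1 is collected").

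SAP 6.2.6 works according to 4.18: "A Kaplan-Meier plot (discontinuation rate) of time to discontinuation of this drug will be generated". A continuation plot is planned as well. No event or censoring definition is given for either. For the Week 40-52 steroid-reduction endpoint, SAP 4.10 says: "Subjects who discontinued or completed administration of this drug before Week 52 will be classified as non-responders".

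**The concern.** A patient who was on the drug at the last record, and about whom nothing later is known, is ordinarily a censored observation in a time-to-discontinuation analysis. Under 4.18 that patient becomes an event dated at the last record. The trigger can be a second form that could not be obtained, not a known decision to stop.

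The discontinuation and continuation curves would then mix stopping the drug with losing the form, and the table of reasons would gain an Unknown group of the same mixed origin. A reader of the outputs could not separate the two. Read together with 4.10, the same patients would also count as failures for steroid reduction.

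**Working it through.** The plan states no figure on this point, so there is none to reproduce.

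**Who is recoded**

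- Week 52 is 364 days (SAP 4.5), so the cut is 364 − 28 = day 336.
- CRF 1 covers Weeks 1 to 24 (Protocol section 7), so a Volume-1-only patient recorded as continuing has an end date at about day 168, or exactly day 168 under the fallback. Since 168 < 336, such a patient inside the 4.18 population is always recoded.
- Patients with both volumes are recoded too if their last recorded administration is before day 336.

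**Effect on the curve**

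If m of n patients at risk at a given time are counted as events instead of censored:

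S_recoded = S_censored × (1 − m/n)

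With recoding at Week 24, D the 52-week discontinuation and v = m/n, the curve shows 1 − (1 − D)(1 − v), where the recoded patients are assumed to stop at the background rate. D and v are assumptions.

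- D = 20%: v = 5% gives 1 − 0.80 × 0.95 = 24%; v = 10% gives 28%; v = 15% gives 32%.
- D = 10%: the same shares give 14.5%, 19% and 23.5%.

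**Error against the truth**

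Let f be the share of all patients who are recoded, q the share of these who really stop by Week 52, and c the background chance of stopping between Week 24 and Week 52. At Week 52:

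- recoding overstates discontinuation by f(1 − q);
- censoring understates it by f(q − c).

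Assume 10% stop by day 168 and c = 10%. The censored curve shows 1 − 0.9 × 0.9 = 19.0%. The recoded curve shows 1 − (0.9 − f) × 0.9.

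| f | Recoded curve | Overstated if q = 10% | if q = 50% | if q = 100% |
|---|---|---|---|---|
| 2% | 20.8% | 1.8 points | 1.0 | 0 |
| 5% | 23.5% | 4.5 | 2.5 | 0 |
| 10% | 28.0% | 9.0 | 5.0 | 0 |
| 20% | 37.0% | 18.0 | 10.0 | 0 |

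Censoring is not free of error either. At f = 10% it understates by 0.10 × (0.50 − 0.10) = 4.0 points if half stopped, and by 0.10 × (1 − 0.10) = 9.0 points if all did. The two errors are equal at q = (1 + c)/2 = 55%.

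**Steroid endpoint**

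If a share g of the denominator is recoded and the rate in the others is r, the reported rate is r(1 − g). With r = 50% (assumed), g = 2%, 5%, 10% or 20% gives 49.0%, 47.5%, 45.0% or 40.0%.

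**The case against.** The case for the plan is that 4.18 is a declared convention. SAP 4.2 labels the group as completed by discontinuation on a logic assessment, and the change history for version 13.0 shows that Volume-1-only cases were considered. If a form is lost because the patient stopped attending, censoring would understate discontinuation. This stands: it is why the result is conditional and why both curves are needed.

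Several stronger readings are tempting but not supported:

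- *Every patient with a missing second form is recoded.* A Volume 2 that is merely pending is not on the 4.2 list, and continuing patients at or after day 336 are unchanged. The scope is not fully clear, because 6.2.6 names the safety analysis population while following 4.18.
- *Discontinuation is certainly overstated.* It is higher than with censoring. Whether it is too high depends on how many recoded patients really stopped, which the documents do not show.
- *There will be an artificial drop at day 168.* That day is a fallback for blank administration status, and patients with no dosing description at all leave the safety set under SAP 4.3.1 (code S3). Recorded last dates may be spread out.
- *The steroid rule is wrong.* The link to 4.18 is inferred, since 4.10 does not cite it. The endpoint covers only baseline doses above 7.5 mg/day. SAP 4.12 bars steroid data after the end of administration, so these patients lack usable Week 40-52 data anyway. Non-responder coding is a defensible conservative choice; dropping them could bias the rate upward.
- *A main result is at risk.* Protocol section 9 does not list persistence, and the person-year rates in SAP 5.5 use treatment dates, not the 4.18 status.

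The Unknown reason makes the group partly visible, but it can mix with other unknown reasons.

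**Conclusion.** The point holds in conditional form. Patients in the completed-observation population who are recorded as continuing, with an end date before day 336, are counted as discontinued in outputs that follow 4.18. That they enter the Kaplan-Meier plots as events is the natural reading of 6.2.6 with 4.18, although 6.2.6 does not define the event.

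The direction relative to censoring is certain. The bias against the truth runs from zero, if all recoded patients stopped by Week 52, up to the full gap between the curves, if they stopped only at the background rate. For the whole curve to be right, and not just its Week 52 value, they must have stopped at about their last recorded date. The size cannot be fixed from the documents, which give no count of recoded patients; every percentage above for discontinuation, recoding and response is an assumption.

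The defect is that the documents show one convention with no censored version and no separate count. Severity is moderate: the persistence curves are affected, but the safety incidence rates are not changed by the recoding itself.

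**What to change.** 1. In Figures 1.02 and 1.021, censor these patients at the last recorded administration date, and say so in SAP 6.2.6. Show the 4.18 recode as a sensitivity curve.
2. In the discontinuation table, take them out of the Unknown reason and give them their own line (continuing at last record, later status unknown), with the count split by Volume-1-only status.
3. For the Week 40-52 steroid endpoint, keep the stated non-responder rule and add one sensitivity row that excludes these patients.

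The cost is SAP wording, a censoring flag and a rerun of a few outputs; no new data are needed. The downside is that figures will differ from earlier interim outputs. Censoring may also understate discontinuation if lost forms reflect stopping, so the two curves should be presented together.
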